## 1. Protocol Summary

Study Title	The Drift-Reduction for Improved FFR using Fiberoptic Technology (DRIFT) study
Device Description	OpSens Medical OptoWire Duex Pressure Wire
Study Design	Prospective, observational, multi-center, single-arm, clinical registry
Objectives	The primary objective of this study is to assess the accuracy, efficacy and durability of the OpSens Medical OptoWire Deux Pressure Wire in the assessment of angiographically intermediate proximal left anterior descending (LAD) stenosis in clinical practice.
Subject Population	Subjects with stable angina, unstable angina, or non-ST segment elevation myocardial infarction (if the LAD lesion is the non-culprit lesion) who are referred to coronary angiography and have an angiographically intermediate proximal LAD stenosis with anatomy amenable to percutaneous intervention. Patients meeting enrollment criteria and had fractional flow reserve (FFR) with the OpSens FFR system and optical coherence tomography (OCT) of the LAD as part of their routine care using a standard of care technique will be eligible for enrollment in this study.
Number of Subjects and Sites	This study will enroll a total of 60 patients at Columbia University Medical Center and St. Francis Hospital.
Primary Endpoint	The primary endpoint is the rate of significant drift, defined as $Pd/Pa < 0.97$ or $> 1.03$ in the pre-percutaneous coronary intervention (PCI) FFR recording.
Secondary Endpoint	
Secondary efficacy endpoints:
 
 
1. The rate of pre-PCI positive FFR (<math>\leq 0.80</math>) in angiographically intermediate proximal LAD lesions.
 
2. The rate of pre-PCI resting <math>Pd/Pa</math> (<math>\leq 0.92</math>) in angiographically intermediate proximal LAD lesions.
 
3. The rate of significant drift defined as <math>Pd/Pa < 0.97</math> or <math>> 1.03</math> with post-PCI FFR recording.
 
4. Pre-PCI OCT correlation (minimum lumen area [MLA] <math>< 2.5 \text{ mm}^2</math>) with FFR (<math>\leq 0.80</math>).
 
5. Pre-PCI OCT correlation with the pullback for distinguishing focal (step-up <math>\geq 0.03</math>) versus diffuse disease defined by pre-PCI resting <math>Pd/Pa</math> pullback.
 
6. Post-PCI OCT correlation (edge dissection [lumen area within the dissection <math>< 4.5 \text{ mm}^2</math>], stent underexpansion [<math>< 4.5 \text{ mm}^2</math>]).
 


	
mm^2 in 3 mm vessel or <math>\leq</math> distal reference lumen area], residual disease outside of stent [minimum lumen area <math><4.5</math> mm^2] with the pullback for distinguishing focal (step-up <math>\geq 0.03</math>) versus diffuse disease defined by post-PCI resting Pd/Pa pullback.
 
7. The rate of discrepancy between FFR and resting physiology indices and its correlation with an OCT derived MLA.
 
Secondary economic endpoints:
 
 
8. Total number of OptoWires used during the procedure.
 
9. Frequency of use of alternative guidewire (workhorse wire) for the procedure.
 
10. Total duration of the procedure.
 
11. Duration of FFR procedure.
 

Procedural Protocol	Patients with an angiographically intermediate proximal LAD lesion, who meet the inclusion and exclusion criteria will be eligible for enrollment in this observational study post-procedure.
Inclusion Criteria	
 
1. Male or female subjects, <math>> 18</math> years of age.
 
2. Patients with stable angina, unstable angina or non-ST segment elevation myocardial infarction (if the LAD lesion is the non-culprit lesion) and in whom an intermediate proximal LAD stenosis (30-80%) with TIMI flow 3 has been identified on angiography.
 
 
NOTE: Patients with multi-vessel disease can be enrolled.
 
 
3. Patients have had FFR and OCT of the LAD with the OpSens FFR system as part of their routine evaluation as standard of care procedure.
 
4. Provides written, informed consent and HIPPA consent to use data in a clinical study.
 

Exclusion Criteria	
General exclusion criteria:
 
 
1. Patients presented with non-ST segment elevation myocardial infarction (NSTEMI) with the LAD involved as the culprit lesion
 
2. ST-elevation myocardial infarction within the past 30 days.
 
3. Hemodynamic instability requiring vasopressor or mechanical circulatory support.
 
4. Prior heart transplant.
 
5. Known left ventricular ejection fraction <math>\leq 40\%</math>
 

	
 
6. LAD supplying akinetic or severely hypokinetic territories if already known based on prior imaging.
 
7. Patients is enrolled in another clinical study that may impact the results of this study.
 
8. FFR not acquired per the instructions for use (IFU) for the OpSens wire.
 
9. LAD Lesion not assessed with OCT.
 
 
Angiographic exclusion criteria:
 
 
1. TIMI grade 2 or lower at baseline angiography.
 
2. Target lesion involves left main (>50% by visual estimation).
 
3. Presence of a chronic total occlusion in any vessel.
 
4. Presence of a side branch <math>\geq 2.75</math> mm with <math>\geq 70\%</math> stenosis in the LAD.
 
5. Bifurcation lesion that resulted in the stent implantation of a side branch.
 

Expected Start Date	February 2018
Enrollment	The enrollment duration is expected to last 5 months.
Follow-up	There is no clinical follow-up.
Regulatory Status	OpSens Pressure Wire received 510(k) clearance from U.S. Food and Drug Administration in March 2016.

### 3. Background

#### 3.1. Fractional flow reserve

Fractional flow reserve (FFR) is an index that quantifies the hemodynamic significance of coronary artery stenosis. FFR is obtained by measuring the ratio between pressure distal to a stenosis and proximally using specialized pressure-measuring guidewires during maximal hyperemia. FFR is considered the standard of reference for clinical decision-making. Clinical outcome studies have shown that medical therapy is preferred for non-hemodynamically significant lesions (FFR >0.80), while coronary revascularization should be considered in cases of significant functional stenosis (FFR ≤0.80). Society guidelines reflect the importance of physiology-guided revascularization, with the ACCF/AHA/SCAI guidelines recommending that FFR is used to guide the treatment strategy in stable coronary lesions. Furthermore, the most recent appropriate use criteria advocates for expanded use of intracoronary physiologic testing.

Nevertheless, for a variety of practical reasons, FFR measurements remain underutilized. Conventional pressure guidewires are limited by three main factors. First, pressure-measuring guidewires have a more complex design than standard guidewires used in percutaneous coronary interventions (PCI). Consequently, traditional pressure guidewires have handling, torquability and lesion crossing characteristics that are suboptimal compared to the mechanical performance of workhorse guidewires. In the FFR cohort in the DEFINE-FLAIR study, only 30.7% of PCI procedures were performed with a pressure wire. A pressure wire with improved handling characteristics to permit use as a workhorse guidewire during interventions fills an important void and improves the likelihood an operator assesses post-intervention FFR by avoiding the need to cross with an additional wire.

Secondly, pressure drift can lead to unreliable FFR values and is a prominent limitation with conventional pressure wires. Drift can occur when air bubbles become trapped in the cavity of the pressure sensor coupled with the inherent thermal and electrical instability of pressure sensors. Signal drift has been reported to occur in as many as 17.5% of FFR cases. Lastly, contrast agents and blood can affect connectivity with conventional pressure wires, reducing its reliability post-stenting.

Therefore, the ability to derive accurate FFR values reliably with minimal drift and with durability to work throughout an entire intervention coupled with the mechanical performance of a workhorse guidewire could have an important impact on daily clinical practice by increasing utilization of FFR both pre- and post-PCI.

The introduction of fiber optic wires can address these issues and improve the performance of FFR wires. The design of the OpSens Medical OptoWire Deux pressure wire combines optimal guidewire performance with the ability to perform FFR measurements. Fiber optic pressure wires may reduce drift, decreasing the number of repeat FFR recordings as well as reducing the number of wire changes. Using the FFR pressure wire for the PCI, thereby avoiding multiple wire exchanges, may have both economic and clinical benefits.

#### 3.2. Rationale for study endpoints and cutoff values

##### 3.2.1. Angiographically intermediate LAD lesions

Lesions in the intermediate range involving the LAD are often undertreated.

Physiologic assessment of these lesions can ensure that the treatment of these lesions is selected and deferred appropriately.

3.2.2. Correlation of Pre-PCI OCT MLA with Pre-PCI FFR

OCT provides accurate and reproducible quantitative assessment of coronary lesions. Prior to revascularization, an OCT MLA  $<2.5 \text{ mm}^2$  can be used to predict FFR  $\leq 0.80$  in the proximal LAD location. Correlation of MLA with a positive FFR value is associated with improved accuracy in the proximal LAD region compared to other coronary segments.

3.2.3. Resting gradient

Resting gradients can be used to predict physiologic significance, however a large discrepancy exists between FFR and resting gradients in locations which supply a large myocardial territory including the left main coronary artery and proximal left anterior descending artery. A resting Pd/Pa  $\leq 0.92$  can be used to predict a significant FFR based on results from the RESOLVE study with a positive predictive value of 89.2% and overall accuracy of 81.5%.

3.2.4. Pullback measurements

Repetitive pullback recordings are a safe and effective method to localize lesions for revascularization. A pullback recording with a pressure wire can also help distinguish the presence of a focal lesion versus diffuse disease. A gradual change in the recording indicates diffuse disease, whereas an abrupt change indicates a focal lesion, and the stenosis can be localized with angiography. A pressure step-up of 0.03 or greater on resting Pd/Pa pullback represents a significant and focal stenosis. Sparse data exists correlating changes in coronary pressure pullback with intravascular ultrasound (IVUS) or OCT lesion assessment.

3.2.5. Post-PCI OCT Assessment

Use of post-PCI MSA as a predictor for future events has been validated in the CLI-OPCI II study. Suboptimal stent deployment based on specific OCT criteria is associated with increased risk for future events. OCT assessment post-PCI with an MSA  $<4.5 \text{ mm}^2$  is an independent predictor of major adverse cardiac events. Edge dissection  $>200 \mu\text{m}$  at the distal stent edge and reference lumen area  $<4.5 \text{ mm}^2$  at either the distal or proximal stent edge is also an independent predictor of worse outcomes.

3.2.6. Post-PCI FFR

Post-PCI FFR may be a useful indicator of optimal PCI, with post-PCI FFR  $\geq 0.9$  associated with a lower risk of repeat PCI and major adverse cardiac events. Data regarding the correlation between post-PCT FFR and intravascular imaging is limited.

3.2.7. Discrepancy between FFR and resting physiology indices

[figure not shown]
Discordance exists between FFR and resting indices such as iFR is related to lesion location. This discordance is most evident in areas of highest flow, including the proximal LAD. Deferring revascularization in the LAD based on

iFR values is associated with significantly decreased events compared with FFR. The correlation between OCT derived MLA and physiologic measurements, in lesions with discordant FFR and resting gradients, has not been previously investigated.

### 3.3. Study Device: OpSens Medical OptoWire Deux Pressure Wire

The OptoWire Deux pressure wire (OpSens Medical, Quebec, Canada) is a novel technology utilizing optical coherence technology to enhance FFR assessment of the coronaries. The OptoWire and OptoMonitor system design allows for simultaneous acquisition of distal pressure from the fiber optic sensor embedded in the OptoWire and aortic pressure from an external pressure transducer to determine an FFR value. The concentric guidewire construction allows for high fidelity pressure measurements during the entire procedure with good steerability and torquability. It is the first hybrid nitinol and stainless steel-based FFR wire designed to improve support for PCI tool delivery and resist kinks. The design of the guidewire allows the OptoWire to function as a workhorse guidewire (Figure 1. Guidewire construction). The optical contact is not affected by blood and allows immediate and reliable signal transmission for FFR measurements. The pressure wire calculates a lesion specific physiological index to determine the hemodynamic severity of an intracoronary lesion.

The OptoWire is FDA approved to measure pressure in coronary vessels during diagnostic angiography and coronary interventions. Anecdotal data suggest fiber optic pressure wires are associated with a significant reduction in signal drift; however, this has yet to be thoroughly validated in clinical practice.

**Figure 1.** Guidewire construction.

## 4. Study Objectives

### 4.1. Study Objectives

The primary objective of this study is to assess the accuracy, efficacy, and durability of the OpSens Medical OptoWire Deux pressure wire in the assessment of angiographically intermediate proximal left anterior descending coronary artery (LAD) stenoses in clinical practice.

### 4.2. Primary Endpoint

The primary endpoint is the rate of significant drift, defined as  $Pd/Pa < 0.97$  or  $> 1.03$  with the pre-PCI FFR recording.

### 4.3. Secondary Endpoints

*Secondary efficacy endpoints:*

1. The rate of pre-PCI positive FFR ( $\leq 0.80$ ) in angiographically intermediate proximal LAD lesions.
2. The rate of pre-PCI resting  $Pd/Pa$  ( $\leq 0.92$ ) in angiographically intermediate proximal LAD lesions.
3. The rate of significant drift defined as  $Pd/Pa < 0.97$  or  $> 1.03$  with post-PCI FFR recording.
4. Pre-PCI OCT correlation (MLA  $< 2.5 \text{ mm}^2$ ) with FFR ( $\leq 0.80$ ).
5. Pre-PCI OCT correlation with the pullback for distinguishing focal (step-up  $\geq 0.03$ ) versus diffuse disease defined by pre-PCI resting  $Pd/Pa$  pullback.
6. Post-PCI OCT correlation (edge dissection [lumen area within the dissection  $\leq 4.5 \text{ mm}^2$ ], stent underexpansion [ $\leq 4.5 \text{ mm}^2$  in 3-mm vessel or  $\leq$  distal reference lumen area], residual disease outside of stent [minimum lumen area  $< 4.5 \text{ mm}^2$ ]) with the pullback for distinguishing focal (step-up  $\geq 0.03$ ) versus diffuse disease defined by post-PCI resting  $Pd/Pa$  pullback.
7. The rate of discrepancy between FFR and resting physiology indices and its correlation with an OCT derived MLA.

*Secondary economic endpoints:*

8. Total number of OptoWires used during the procedure.
9. Frequency of use of alternative guidewire (workhorse wire) for the procedure.
10. Total duration of the procedure

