## 11. Duration of the FFR procedure

## 5. Study Design and Population

This study is designed as a prospective, observational, multi-center, single-arm, clinical registry to estimate the ischemic burden of angiographically intermediate proximal LAD stenosis in clinical practice using the OpSens Medical OptoWire Deux FFR system. Subjects with stable angina or unstable angina who are found to have an intermediate proximal LAD stenosis on coronary angiography with anatomy amenable to PCI and underwent physiological lesion assessment with the OptoWire Deux pressure wire and OCT as part of their routine procedures using standard of care techniques will be enrolled. Patients meeting enrollment criteria will be offered the opportunity to enroll in this observational registry post-procedure. All patients enrolled in this study are expected to be evaluated and treated using a standard of care technique. This study will enroll a total of 60 patients at Columbia University Medical Center and St. Francis Hospital.

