## 8. Statistical Considerations

This is a prospective, observational, multi-center, clinical study designed to estimate the ischemic burden of angiographically intermediate proximal LAD stenosis using FFR. Efficacy will be measured using the OpSens FFR system.

The study's primary endpoint is the rate of significant drift, defined as FFR <0.97 or >1.03 with the pre-PCI FFR recording using the OpSens OptoWire Deux pressure wire system.

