### 8.1. Statistical Analysis and Analysis Sets

All statistical analyses will be performed using SAS (SAS Institute Inc., Cary, NC). Patient data listings and tabular presentations of results will be provided listing the mean, standard deviation, median, minimum, maximum, and number of subjects for continuous data, or in tables listing count and percentage for categorical data, where appropriate.

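### Significant drift is counted as an outcome, but no rule says how drifted recordings enter the other physiology endpoints, so by default they are included

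*Combined protocol and SAP*

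**What the plan says.** **Drift as an outcome.** Section 4.2 of the protocol states: "The primary endpoint is the rate of significant drift, defined as" Pd/Pa below 0.97 or above 1.03 on the pre-PCI FFR recording. Secondary endpoint 3 in Section 4.3 applies the same limits after PCI. Section 8 words the primary endpoint differently: "defined as FFR <0.97 or >1.03 with the pre-PCI FFR recording".

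**Other physiology endpoints (Section 4.3).**
- Endpoint 1, "The rate of pre-PCI positive FFR", uses FFR of 0.80 or less.
- Endpoint 2, "The rate of pre-PCI resting" Pd/Pa, uses 0.92 or less.
- Endpoint 4 relates OCT minimum lumen area to FFR at 0.80.
- Endpoint 7 is the FFR versus resting-index discrepancy and its relation to lumen area.
- Endpoints 5 and 6 relate OCT findings to a resting pullback step-up of at least 0.03, before and after PCI.

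None of these is restricted by drift status.

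**Why drift matters.** Section 3.1 says that "pressure drift can lead to unreliable FFR values and is a prominent limitation with conventional pressure wires", and gives the only drift rate in the document: "Signal drift has been reported to occur in as many as 17.5% of FFR cases".

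**Analysis rules.** Section 8.1 mentions analysis sets in its title but defines none. It names the software and the descriptive summaries: "Patient data listings and tabular presentations of results will be provided". On sample size, Section 5 says: "This study will enroll a total of 60 patients at Columbia University Medical Center and St. Francis Hospital".

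**The concern.** The study's primary endpoint identifies recordings with an error above 0.03. The same recordings then supply the values that are classified at 0.80 and 0.92. The protocol treats a difference of 0.03 as meaningful elsewhere, since it is the step-up that marks a focal lesion (Section 3.2.4).

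Sections 5 and 8 describe the study as designed to estimate the ischemic burden of these lesions, and endpoint 1 is that estimate. If drift tends to go one way, the FFR-positive and resting-positive rates are biased, and a confidence interval does not cover that. If it goes both ways, patients are misclassified in the OCT-FFR and discordance analyses. With no rule written down, the choice to keep or drop flagged recordings could also be made after the results are seen.

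**Working it through.** The plan gives no figure to reproduce: 60 patients are stated without a hypothesis, precision target or expected drift rate for this wire.

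**Step 1: does any rule remove or correct flagged recordings?**
- General exclusion 8 (Section 5.3) removes FFR not acquired per the instructions for use. It does not mention drift, and it cannot remove all drifted recordings because the primary endpoint must count them.
- Sections 6.5 and 11.4 send tracings to a core laboratory but give no rejection rule.
- Section 3.1 mentions repeat recordings as something the wire may reduce. No section says which recording counts after a repeat.

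So inclusion is the default.

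**Step 2: how many flagged recordings to expect.** Expected number = 60 × drift rate; chance of at least one = 1 − (1 − rate)^60. The 17.5% is from Section 3.1; 2%, 5% and 10% are assumptions.

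| Drift rate | Expected of 60 | Chance of at least one |
|---|---|---|
| 2% | 1.2 | 70% |
| 5% | 3 | 95% |
| 10% | 6 | 99.8% |
| 17.5% | 10.5 | >99.9% |

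**Step 3: chance that a flagged recording changes class.** Assumptions, none from the document: true FFR normal with mean 0.80 and SD 0.07 to 0.11; true resting Pd/Pa normal with mean 0.92 and SD 0.05; absolute offset d uniform on 0.03-0.06 or 0.03-0.10, fully present in the analysed reading. With the mean on the cut-off, P(change) is the average over d of Φ(d/SD) − 0.5.

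| Index | SD | d on 0.03-0.06 | d on 0.03-0.10 |
|---|---|---|---|
| FFR at 0.80 | 0.07 | 23.8% | 31.4% |
| FFR at 0.80 | 0.11 | 15.8% | 21.9% |
| Resting Pd/Pa at 0.92 | 0.05 | 31.2% | 38.6% |

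The ranges are therefore 15.8-31.4% for FFR and 31.2-38.6% for resting Pd/Pa.

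**Step 4: patients changing class** = 60 × drift rate × P(change).
- FFR at 5%: 60 × 0.05 × 0.158 = 0.47, to 60 × 0.05 × 0.314 = 0.94.
- FFR at 17.5%: 60 × 0.175 × 0.158 = 1.7, to 60 × 0.175 × 0.314 = 3.3 (2.8% to 5.5% of patients).
- Resting at 5%: 0.05 × 0.312 = 1.6%, to 0.05 × 0.386 = 1.9% of patients.
- Resting at 17.5%: 0.175 × 0.312 = 5.5%, to 0.175 × 0.386 = 6.8% of patients.

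**Step 5: sensitivity to the assumptions.**
- With an FFR mean of 0.75 or 0.85 and random direction, the FFR range falls to 14-26%.
- If only half the offset was present at the resting reading, the resting range falls to 17-24%.
- A wider grid, with all drift in the worse direction (FFR mean 0.78-0.85, SD 0.06-0.10, offset 0.03-0.08), shifts the FFR-positive rate by 0.2-1.0 points at 2% drift and 2.0-8.6 points at 17.5%.

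**Step 6: direction.** If all drift goes one way, the FFR-positive rate shifts by the percentages in Step 4. If direction is balanced and the mean sits on the cut-off, upward and downward changes cancel in expectation. Away from the cut-off a small remainder is left. For example, with mean 0.85, SD 0.07 and d on 0.03-0.06, 23.4% change one way and 14.9% the other. The net is (23.4 − 14.9)/2 = 4.25% of flagged recordings, or 0.7 points at 17.5% drift.

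**Step 7: pullback endpoints.** A step-up is a difference between two readings in one pullback, so a constant offset largely cancels. Drift that changes during the pullback does not.

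**Step 8: precision cost of dropping flagged recordings.** Exact (Clopper-Pearson) 95% half-width for a rate near 50%: 13.2 points at n = 60, 13.5 at n = 57 (5% drift), 13.9 at n = 54 (10%), and 14.5-14.6 at n = 49-50 (17.5%). The largest loss is 14.6 − 13.2 = 1.4 points.

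**The case against.** The strongest reply is that silence is not a rule. A reader might infer that the plan requires drifted recordings to be analysed. It does not say so: a repeat may replace a drifted recording, and the core laboratory's procedures and the instructions for use are not in the document. That stands as to wording, but nothing written closes the gap.

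A reader might also infer that the protocol itself calls flagged recordings unreliable. Section 3.1 says only that drift can have that effect, and says it of conventional wires.

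Nor are all these endpoints classified at 0.80 or 0.92. Endpoints 5 and 6 use a step-up, and endpoint 7 states no resting cut-off.

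The size is also open to challenge, and fairly. Placing the means on the cut-offs gives high figures; 17.5% is an upper figure from earlier cases; Section 3.3 cites anecdotal evidence of less drift with fiber optic wires; and no direction of drift is documented. Even the largest shift, 8.6 points, is below the sampling half-width of about 13.

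On discordance, a shared offset moves both indices the same way. With means at the cut-offs, SDs of 0.09 and 0.05, an assumed correlation of 0.6-0.8 and random direction, simulated discordance among drifted recordings fell from 20-30% to 16-25%. That is still an error, but not simply added discordance.

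Finally, an all-recordings main analysis suits an objective framed around clinical practice. That stands: which version is primary is the sponsor's choice, but it should be made in advance.

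**Conclusion.** The point holds as a missing handling rule with a default that includes flagged recordings. It bears mainly on endpoints 1, 2, 4 and 7, and less on 5 and 6. Calling flagged values off by more than 0.03 assumes that the drift check should read 1.00; the document does not say where or when it is read.

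The effect is small if the wire rarely drifts: under one patient in 60 changes FFR class at 5%. It is modest at 17.5%: 1.7-3.3 patients. The resting rate is more sensitive if the full offset was present at that reading. A material bias in the rates requires a preferred direction, for which the document gives no evidence; without one, the main effect is misclassification. These figures rest on assumed distributions and should be read as orders of magnitude. The change is worth making because it costs little and, even at 5% drift, there is a 95% chance that at least one recording will need the rule.

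**What to change.** 1. **Reconcile the drift definition first.** Sections 1 and 4.2 use Pd/Pa; Section 8 uses FFR. Read literally, Section 8 flags every FFR of 0.80 or less, so excluding flagged recordings would delete every positive FFR. State also where and when the drift value is read.
2. **Report two versions.** Give endpoints 1, 2, 4 and 7, and for completeness 5 and 6, for all recordings and for recordings without significant drift. Use the post-PCI drift result for endpoint 6.
3. **Specify in advance** which version is primary, which recording counts after a repeat, and the denominator of each version. Report how many patients change class when a repeat without significant drift is available for comparison.

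**Cost.** A short addition to Section 8.1 and a second table column, once the definition is settled. The drift-free version loses about 3 of 60 patients at 5% drift or 10 of 60 at 17.5%, and its half-width grows by at most about 1.4 points. The all-recordings version loses nothing.

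### Endpoint 6 reduces the post-PCI resting pullback to a yes/no step of 0.03 that the plan never matches to its 4.5 mm² OCT limit, so the split may miss borderline findings and discards information; analyse the step size as well

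*Combined protocol and SAP*

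**What the plan says.** Endpoint 6 in section 4.3 sets post-PCI OCT findings against the resting pullback. The OCT findings are:

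- edge dissection, with a lumen area limit of 4.5 mm²;
- stent underexpansion, by a 4.5 mm² limit in a 3 mm vessel or by a stent area no larger than the distal reference lumen area;
- "residual disease outside of stent [minimum lumen area" below 4.5 mm²].

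The pullback side has two categories: focal, meaning a step-up of at least 0.03, "versus diffuse disease defined by post-PCI resting" Pd/Pa pullback.

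The cut-offs are justified separately:

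- Section 3.2.4: "A pressure step-up of 0.03 or greater on resting Pd/Pa pullback represents a significant and focal stenosis". The same section says that data linking pullback to intravascular imaging are sparse.
- Section 3.2.5: a stent area below 4.5 mm² "is an independent predictor of major adverse cardiac events".
- Section 3.2.2: before PCI, an OCT lumen area below 2.5 mm² "can be used to predict FFR" of 0.80 or less in the proximal LAD.
- Section 3.2.3: a resting Pd/Pa of 0.92 or less "can be used to predict a significant FFR based on results from the RESOLVE study". The section puts the accuracy of that cut-off at 81.5% and its positive predictive value at 89.2%.

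Section 8 provides descriptive summaries only. It names no method for this correlation and gives no area-to-gradient relation.

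**The concern.** One cut-off comes from clinical events and the other from pullback physiology. The plan gives no reason to expect a 4.5 mm² lumen to produce a resting step of 0.03. If the usual step at the area limit is smaller, borderline OCT findings land in the non-focal category, and the only other category on offer is diffuse. If it is larger, many OCT-negative vessels are called focal. Either way the two-by-two table weakens a relation that the tracings could show.

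What is at stake is how a weak result would be read. Because the plan itself calls the evidence sparse, a reader could take a weak association as showing that OCT findings after stenting have no pressure effect, when part of the weakness came from where the split was placed.

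**Working it through.** The plan states no expected step at 4.5 mm², so there is no figure of its own to reproduce. The check asks what step is plausible there and what the split costs.

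**Inputs from the documents.** Lumen area 2.5 mm² paired with FFR 0.80 (3.2.2). Resting Pd/Pa 0.92 paired with FFR 0.80 (3.2.3), a resting drop of 1 − 0.92 = 0.08. Step cut-off 0.03 (3.2.4). Area limit 4.5 mm² and a 3 mm vessel, area 7.07 mm² (4.3).

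**Assumptions, not in the documents.** The law linking area to pressure loss; equal lesion length and equal resting flow before and after PCI; the share of the 0.08 arising at one site (all or half); a 3.5 mm reference (9.62 mm²) as an alternative.

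**Step 1: expected step at 4.5 mm².**

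- Power law: 0.08 × (2.5/4.5)^k. With k = 2, 0.08 × 0.3086 = 0.0247. With k = 1.5, 0.033. With k = 1, 0.044.
- Expansion loss: 0.08 × [(1/4.5 − 1/Aref)/(1/2.5 − 1/Aref)]². With Aref = 7.07, 0.08 × (0.0808/0.2585)² = 0.0078. With Aref = 9.62, 0.0128.
- If half the loss is local, the k = 2 and expansion values halve: 0.012, 0.0039 and 0.0064.

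The range is about 0.004 to 0.044.

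**Step 2: area at which the step reaches 0.03.** For k = 2, 2.5 × √(0.08/0.03) = 4.08 mm². If half the loss is local, 2.5 × √(0.04/0.03) = 2.89 mm². For expansion loss, 3.34 mm² (3.0 mm reference) or 3.51 mm² (3.5 mm). For k = 1.5 and k = 1 it is 4.81 and 6.67 mm², above the OCT limit.

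**Step 3: smaller flagged lumens, k = 2.** 4.0 mm² gives 0.031, 3.5 gives 0.041 and 3.0 gives 0.056. Under this law only lumens of about 4.08 to 4.5 mm² fall short.

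**Step 4: fragility.** The k = 2 result crosses 0.03 at 4.5 mm² if the exponent falls below 1.67, if length × flow is 0.03/0.0247 = 1.215 times that of the anchor lesion, or if the anchor drop is 0.097 instead of 0.08.

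**Step 5: the distal-reference criterion.** This can flag stents above 4.5 mm². Taking 6 mm² as an illustration, the step is 0.014 (k = 2), 0.022 (k = 1.5), 0.033 (k = 1) or under 0.004 (expansion loss).

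**Step 6: split against measured step.** Illustrative simulation, 1,500 runs, with assumed inputs: 30 PCI patients, post-PCI minimum area mean 5.5 and SD 1.5 mm², step-reading SD 0.01, OCT-positive at 4.5 mm² or below. Fisher's test was used on the split and Mann–Whitney on the measured step.

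| Assumed law | Step at 4.5 mm² | Power, 0.03 split | Power, measured step |
|---|---|---|---|
| k = 2 | 0.025 | 88% | 95% |
| k = 2, half local | 0.012 | 35% | 67% |
| Expansion, 3.0 mm | 0.008 | 61% | 89% |
| Expansion, 3.0 mm, half local | 0.004 | 16% | 57% |
| Expansion, 3.5 mm | 0.013 | 74% | 93% |
| Expansion, 3.5 mm, half local | 0.006 | 24% | 64% |
| k = 1.5 | 0.033 | 83% | 96% |
| k = 1 | 0.044 | 24% | 95% |

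Repeat runs moved these by up to about five points. The order never changed, including when reading noise was raised. The share of OCT-flagged vessels called focal was 69% for k = 2, 34% for expansion with a 3.0 mm reference, and 23% and 14% for the same two laws with half the loss local. Under k = 1 the split fails in the other direction: 62% of OCT-negative vessels are called focal.

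**The case against.** A reader might infer that, on the plan's own cut-offs, a 4.5 mm² lumen must fall below 0.03, so that endpoint 6 cannot register the findings it studies and is biased towards no relation. The documents do not support that, for four reasons.

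- The 0.025 needs a pressure-loss law, a length, a flow and a local share that the plan does not give. Plausible alternatives exceed 0.03.
- The 2.5 mm² and 0.92 values are two separate classifiers of the same FFR limit, not a measured area-and-gradient pair. Section 3.2.3 itself warns that "a large discrepancy exists between FFR and resting gradients in locations which supply a large myocardial territory", naming the proximal LAD among them. The 0.08 is a whole-vessel drop, not a focal step.
- The 4.5 mm² value is an upper limit, and smaller lumens reach 0.03 under the same law. Even there, 69% of flagged vessels are called focal.
- The distal-reference criterion has no 4.5 mm² limit, so a calculation at that area does not cover it.

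Those points stand. It can also be said that the split answers the question asked, namely whether OCT findings coincide with a step of the size called focal; that different rationales for two cut-offs are not an error in themselves; and that the simulation inputs are invented and generate the step from area, which favours the continuous analysis. Section 8 plans no test or power for this endpoint. All of this is fair, and it is why the 0.03 table should stay. It does not remove the loss of information: the step has to be read to apply the split, and the advantage of using its size did not depend on which law was assumed.

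**Conclusion.** The point holds as a possible loss of sensitivity and power in one secondary endpoint. The plan does not match the 0.03 step to the 4.5 mm² limit. Near that limit the expected step could lie on either side of the cut-off, so the focal/diffuse split may miss borderline findings, and it discards the size of the step in every case. A bias of known size is not shown, because it depends on the distribution of post-PCI areas, which the plan does not give. The simulated gains, from 7 points (95% against 88%) to 71 points (95% against 24%), are illustrations under assumed inputs; only their direction was consistent. This is a cheap improvement, not a flaw that invalidates the endpoint.

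**What to change.** In section 4.3 (endpoint 6) and section 8, add an analysis of the size of the resting Pd/Pa step, read by the core lab across the OCT-flagged segment, as a continuous value. Compare it between OCT-positive and OCT-negative vessels, and relate it to lumen area. State which segment is read in OCT-negative vessels. Keep the focal/diffuse table at 0.03. Add a sentence saying that absence of a step of 0.03 or more does not show an OCT finding to be physiologically silent.

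The cost is wording and one core-lab reading. Section 6.4 already collects the pullback tracing, the OCT images and the cine of the sensor position, and section 6.5 sends FFR tracings and OCT images to the core lab. Since 6.5 does not name the pullback, confirm that it is included. No patients or procedures are added. The downside is that steps of 0.01 to 0.02 lie close to reading noise, so individual values will be imprecise and the result is best read as a group comparison.
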